Patients in Cohort 3 also received a single iv dose of 50 IU/kg Nuwiq in order to compare the bioavailability of sc OCTA101 with those of Nuwiq (the FVIII part of OCTA101) injected intravenously (iv). The treatment sequence was Nuwiq followed by OCTA101. Dose

Name of Sponsor/Company: Octapharma AG		
Name of Investigational Product: OCTA101 (Human-cl rhFVIII and recombinant human von Willebrand Factor fragment dimer)	Protocol Identification Code: SubQ8-01	silo
Name of Active Ingredient: Coagulation factor VIII	Date of Final Protocol: 30-Jul-2021	

proportionality of OCTA101 was evaluated after single sc administration of three different doses (20 IU/kg, 40 IU/kg and 60 IU/kg) in 4 additional patients (Cohort 5).

A PK assessment was performed in patients from Cohorts 1 and 2 who completed their 3-month daily injection period.

Following completion of the PK assessments in Cohort 3 and 1-month into OCTA101 daily prophylaxis in this cohort, the study was put on hold due to inhibitor development in a second patient (in Cohort 2).

Due to the study hold, patients in Cohort 3 were switched to prophylaxis with Nuwiq after having received 1-month of OCTA101 daily prophylaxis. Patients in Cohort 3 completed the study when their overall time on daily prophylaxis (OCTA101 + Nuwiq) reached 3 months. By the time of preparation of protocol version 8.0, Cohorts 1, 2 (with the exception of 1 patient with FVIII inhibitors who entered ITI treatment with Nuwiq), 3, and 5 were completed.

With the agreement of the DMC, it was decided to proceed with the study, introducing the following changes to the study design. Cohort 4 was cancelled and Cohort 5 was cut from 8 patients to 4.

A new cohort (Cohort 6) was initiated for 16 evaluable patients. In this cohort, patients have an initial 4 to 6-week run-in treatment period with Nuwiq iv prophylaxis followed by 12.5 IU/kg OCTA101 sc daily prophylaxis for >3 up to 6-7 months. With DMC agreement, the patients will then proceed to 25 IU/kg OCTA101 sc daily prophylaxis for 6-7 months. Based on the results of both dosing phases, a 40 IU/kg OCTA101 will be considered. Cohort 6 is planned to proceed as follows:

- Following completion of the run-in period with Nuwiq iv prophylaxis, 3 patients started daily dosing with 12.5 IU/kg OCTA101 sc.

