- After 3 months of treatment with OCTA101, the patients had their 3-month follow-up visit. During the 2 to 3 weeks waiting for all relevant results, especially FVIII inhibitor testing results, these patients continued on daily dosing with 12.5 IU/kg OCTA101 sc.
- DMC agreed that further patients can start their daily prophylaxis with OCTA101, up to 16 patients proceeded with 12.5 IU/kg OCTA101. After further 3 months, following DMC data review, the first 3 patients of this cohort were planned to start on daily dosing with 25 IU/kg OCTA101 sc for 6-7 months. The remaining patients were planned to follow after a further 3 months, after DMC data review.
- Patients reporting two spontaneous bleeding episodes will be switched to the next higher dose level after having completed at least 3 months with 12.5 IU/kg OCTA101 daily treatment: they will start daily dosing with 25 IU/kg OCTA101 sc.

Name of Sponsor/Company: Octapharma AG		
Name of Investigational Product: OCTA101 (Human-cl rhFVIII and recombinant human von Willebrand Factor fragment dimer)	Protocol Identification Code: SubQ8-01	silor
Name of Active Ingredient: Coagulation factor VIII	Date of Final Protocol: 30-Jul-2021	

- Depending on the results of the 12.5 IU/kg and 25 IU/kg OCTA101 treatment phases, the initiation of a 40 IU/kg OCTA101 phase will be considered together with the DMC.
- Bleeding episodes will be controlled with the use of Nuwiq during the entire duration of treatment in Cohort 6.

The cohorts are summarized as follows:

• Cohort 1: 50 IU/kg OCTA101 (n=4): Single-period investigation with a single sc dose of 50 IU/kg OCTA101 profiled up to 72 hours after dosing.

DMC assessment after last patient of Cohort 1. If ok, proceed with Cohort 2, and also with daily prophylactic dosing (approximately 40-60 IU/kg) for 3 months (initially with Nuwiq but then with OCTA101 if advised by the DMC). Patients from Cohort 2 and 3 may also start their daily prophylactic dosing for 3 months immediately after collection of the last PK sample.

- Cohort 2: 100 IU/kg OCTA101 (n=4): Single-period investigation with a single sc dose of 100 IU/kg OCTA101 profiled up to 96 hours after dosing. DMC assessment after last patient of Cohort 2. If ok, proceed with Cohort 3.
- Cohort 1 and 2: PK assessment after 3-month daily dosing (n=8): single-period investigation with a single sc dose of 50 IU/kg OCTA101 profiled up to 120 hours after dosing for FVIII and up to 21 days for OCTA12.

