Independent expert evaluation by the DMC has steered study progress for the stepwise dosage increments by cohort and the progression of patients from the first three cohorts to 3-month daily dosing. In addition, the DMC has advised on changes of the proposed dosage for the assessment of bioavailability (Cohort 3) and dose-proportionality (Cohort 5) and changes in the schedule of PK blood sampling and/or the duration of profiling without substantially increasing the total amount of blood to be sampled. Based on the observation of a second patient with inhibitors in Cohort 2, the DMC recommended placing the study on hold. The DMC recommended restarting the study with the implementation of Amendment 3, which cancelled Cohort 4, cut Cohort 5 to 4 patients instead of the planned 8, and introduced Cohort 6 investigating OCTA101 sc prophylaxis over 6-7 months of treatment per dose level following a run-in period with Nuwiq iv prophylaxis. The DMC will continue to be involved in the further conduct of the study.

This study started in Q2 2019 and is planned to be completed by Q3 2022.

**Number of Patients:** N = 36 evaluable in total (16 evaluable patients in Cohort 6)

Name of Sponsor/Company: Octapharma AG		
Name of Investigational Product: OCTA101 (Human-cl rhFVIII and recombinant human von Willebrand Factor fragment dimer)	Protocol Identification Code: SubQ8-01	sil
Name of Active Ingredient: Coagulation factor VIII	Date of Final Protocol: 30-Jul-2021	

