A new cohort (Cohort 6) was planned with 16 evaluable patients. In this cohort, around 18-20 patients (to compensate for possible early drop-outs) were planned to start with an initial 4 to 6-week run-in treatment period with Nuwiq iv prophylaxis followed by 12.5 IU/kg OCTA101 sc daily prophylaxis for >3 up to 6-7 months. With DMC agreement, the patients were planned to proceed to 25 IU/kg OCTA101 sc daily prophylaxis for 6-7 months. Based on the results of both dosing phases, a 40 IU/kg OCTA101 were planned to be considered.

Cohort 6 was planned to proceed as follows:

Propert

Following completion of the run-in period with Nuwig iv prophylaxis, 3 patients (one • screened patient withdrew consent after Nuwiq run-in phase) started daily dosing with 12.5 IU/kg OCTA101 sc.

Study Protocol No. SubQ8-01, Version 9.0 CONFIDENTIAL

- After 3 months of treatment with OCTA101, the patients will have their 3-month followup visit. During the 2 to 3 weeks waiting for all relevant results, especially FVIII inhibitor testing results, these patients will continue on daily dosing with 12.5 IU/kg OCTA101 sc.
- If the DMC determines that further patients can start their daily prophylaxis with OCTA101, at least 16 patients will proceed with 12.5 IU/kg OCTA101. After a further 3 months, following DMC data review, the first 3 patients of this cohort will start on daily dosing with 25 IU/kg OCTA101 sc for 6-7 months. The remaining patients will follow after a further 3 months, after DMC data review.
- Patients reporting two spontaneous bleeding episodes will be switched to the next higher dose level after having completed at least 3 months with 12.5 IU/kg OCTA101 daily treatment: they will start daily dosing with 25 IU/kg OCTA101 sc.
- Depending on the results of the 12.5 IU/kg and 25 IU/kg OCTA101 treatment phases, the initiation of a 40 IU/kg OCTA101 phase will be considered together with the DMC.
- Bleeding episodes will be controlled with the use of Nuwig during the entire duration of treatment in Cohort 6.

The cohorts are summarized as follows:

- Cohort 1: 50 IU/kg (n=4): single-period investigation with a single sc dose of 50 IU/kg OCTA101 profiled up to 72 hours after dosing.
- Cohort 2: 100 IU/kg (n=4): single-period investigation with a single sc dose of 100 IU/kg OCTA101 profiled up to 96 hours after dosing.

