#### **Dose and Dosing Schedule** 5.4

The following will be administered at the study site by trained personnel:

Cohort 1: Single injection of OCTA101 50 IU/kg sc with 72 hours of observation.

- Cohort 2: Single injection of OCTA101 100 IU/kg sc with 96 hours of observation.
- Cohort 1 and 2: PK assessment after 3-month daily dosing: Single injection of OCTA101 50 IU/kg sc with 120 hours of observation for FVIII and 21 days of observation for OCTA12.
- Cohort 3: Single injection of Nuwiq 50 IU/kg iv with 72 hours of observation, followed by single injection of OCTA101 50 IU/kg sc administered into the abdomen with 72 hours of observation.
- Cohort 4: (Cancelled) Single injection of OCTA101 50 IU/kg sc administered into the thigh with 72 hours of observation.
- Cohort 5: Single injection of OCTA101 20 IU/kg sc with 72 hours of observation, followed by single dose of OCTA101 40 IU/kg sc with 72 hours of observation, followed by single dose of OCTA101 60 IU/kg sc with 72 hours of observation.
- Cohort 6: 4-6 weeks prophylactic run-in treatment phase with ~30 IU/kg Nuwiq iv, given 3 x weekly, followed by 2 (probably 3) phases of 6-7 months daily injection with OCTA101, first 12.5 IU/kg, followed by 25 IU/kg daily (and probably 40 IU/kg). No wash-out periods are required between the treatment phases. Patients reporting two spontaneous bleeding episodes during the 12.5 IU/kg treatment phase may immediately switch to the 25 IU/kg daily, if they have completed at least 3 months with 12.5 IU/kg. Nuwiq (according to SmPC) is used to control bleeding episodes, if any.

In all cases, the minimum number of injections required to provide the required dose must be administered. If multiple injections are needed, then they should not be administered at the same spot. The PK doses were to be achieved as accurately as possible with the available vial strengths as a single injection; it was permitted to daily alternate the vial size, (e.g. 3000 IU on one day 1, 5000 IU on day 2, 3000 IU on day 3, 5000 IU on day 4 etc.).

OCTA101 will be administered by sc injection into the abdomen or thigh (see Appendix 1 in Section 13.a), whereby for Cohorts 1 and 2 the choice is up to the investigator and patient, in Cohort 3 all administrations of OCTA101 will be into the abdomen, in Cohort 5, four patients each will consistently be injected with OCTA101 either in the abdomen or in the thigh at all three dose levels.

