#### 9.1 **Determination of Sample Size**

The sample size was determined based on pre-clinical findings and clinical reasoning, and was discussed with the FDA. No formal sample size calculation was performed.

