The total annualized bleeding rate, the spontaneous annualized bleeding rate, the traumatic annualized bleeding rate, the total annualized treated bleeding rate, the spontaneous annualized treated bleeding rate, and the annualized joint bleeding rate during daily se treatment with OCTA101 will be presented for patients in the FAS and PP set in Cohort 6, grouped by dose level of daily OCTA101 dosing. For the daily dosing period of Cohorts 1 to 3, no bleeding rates were calculated. The observation period was considerably shorter than planned due to the study stop. Bleedings occurred only in patients who had developed antibodies or after the end of the daily dosing period.

All other data collected for BEs, efficacy assessments at the end of BEs will be analyzed descriptively. The proportion of BEs successfully treated with Nuwiq will be presented. Summaries on patient levels will be detailed in the SAP as needed. All data collected will be listed.

FVIII:C and OCTA12 trough and peak plasma levels during daily dosing will be analyzed descriptively.

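### Cohort 6: two spontaneous bleeds can end time at 12.5 IU/kg after month 3, so whole-phase bleeding rates by dose level can be distorted; add a first-3-month rate and the number of early switchers.

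*Protocol*

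**What the plan says.** Protocol 9.2.2 lists six annualized bleeding rates (total, spontaneous, traumatic, total treated, spontaneous treated, joint) that "will be presented for patients in the FAS and PP set in Cohort 6, grouped by dose level of daily OCTA101 dosing". The statistical section of the Study Outline repeats this and adds a descriptive comparison with the 6 months before the study. Neither place writes a 12.5 versus 25 IU/kg contrast.

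The dosing plan is "12.5 IU/kg OCTA101 sc daily prophylaxis for >3 up to 6-7 months"; with DMC agreement, patients then "proceed to 25 IU/kg OCTA101 sc daily prophylaxis for 6-7 months". The cohort summaries in the Study Outline and Section 3.2 give the first phase as more than 3 and up to 6 months.

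The early switch is worded in two ways:
- Study Outline: "Patients reporting two spontaneous bleeding episodes will be switched to the next higher dose level after having completed at least 3 months" at 12.5 IU/kg. Section 3.2 agrees: "Patients reporting two spontaneous bleeding episodes will be switched to the next higher" dose level.
- Section 5.4: such patients "may immediately switch to the 25 IU/kg daily, if they have completed at least 3 months with 12.5 IU/kg".

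The target is "16 evaluable patients in Cohort 6", and Section 9.1 states "No formal sample size calculation was performed".

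No estimator is fixed for Cohort 6. SAP Sections 4 and 5.2 put that cohort out of scope and refer to a separate SAP. For the earlier cohorts, SAP 8.6.3 pools bleeds and pools time. Neither document says how the bleeds and time of early switchers are to be handled.

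**The concern.** After month 3, the event being counted decides how long a patient is observed at 12.5 IU/kg. This acts in two opposite ways.

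- **Averaging patient rates.** Observation stops on a bleed, which inflates the individual rate. A patient whose second bleed comes at month 4 scores 2/(4/12) = 6.0 per year. Watched to 6.5 months with no further bleed, he would score 2/(6.5/12) = 3.7.
- **Pooling bleeds and time.** Frequent bleeders leave early and contribute less time, so the pooled rate leans towards infrequent bleeders.

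The by-dose table is the planned display of how well each dose prevents bleeding. Section 3.2 makes a 40 IU/kg phase depend on the results of the two earlier phases, and Section 1.3 says the study is to show whether the FVIII:C levels reached protect against bleeding. The planned comparison with the pre-study period would use the same 12.5 IU/kg figure.

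**Working it through.** The documents contain no Cohort 6 rate, power or effect size, so there is no figure of the plan to reproduce. The check asks what the grouped table would show if both doses had the same true bleeding rate.

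**Inputs from the documents:** 16 patients; switch at the later of a = 3 months (0.25 year) and the second spontaneous bleed; otherwise T = 6.5 months (0.5417 year) at 12.5 IU/kg, the midpoint of 6-7; then 6.5 months at 25 IU/kg.

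**Assumptions:** spontaneous bleeds are Poisson; mean rate 1 to 8 per year (ABR), the same at both doses; patient rates gamma-distributed with CV 0 to 1.5; every eligible patient switches.

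**Step 1: expected time at 12.5 IU/kg for a patient with rate λ.** He is still there at time s > a only if he has had at most one bleed, so

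E[t] = a + ∫ from a to T of (1 + λs)e^(−λs) ds = a + (2/λ + a)e^(−λa) − (2/λ + T)e^(−λT).

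- λ = 1: 0.25 + 2.25 × 0.7788 − 2.5417 × 0.5818 = 0.524 year
- λ = 7: 0.25 + 0.5357 × 0.1738 − 0.8274 × 0.0226 = 0.324 year

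**Step 2: pooled rate.** The switch is a stopping time, so E[y] = λE[t]. If all patients share one λ, E[y]/E[t] = λ and there is no large-sample bias. If half have λ = 1 and half λ = 7 (true mean 4), the large-sample pooled rate is (1 × 0.524 + 7 × 0.324)/(0.524 + 0.324) = 2.795/0.848 = 3.30 per year, which is 18% too low.

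**Step 3: simulation, at least 20,000 trials of 16 patients per row, no dose effect.** Entries are bias of the 12.5 IU/kg rate.

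| ABR | CV | Switch early | Pooled | Mean of patient rates | First 3 months |
|---|---|---|---|---|---|
| 1 | 0 | 10% | +1% | +20% | 0% |
| 1 | 0.7 | 12% | −2% | +21% | 0% |
| 2 | 0 | 29% | +1% | +27% | 0% |
| 2 | 1 | 27% | −11% | +21% | 0% |
| 4 | 0 | 64% | +1% | +25% | 0% |
| 4 | 1 | 47% | −17% | +15% | 0% |
| 8 | 1 | 66% | −20% | +7% | 0% |
| 8 | 1.5 | 51% | −29% | +5% | 0% |

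At ABR 4 and CV 1, the pooled 12.5 IU/kg rate falls below the 25 IU/kg rate in 76% of trials although the doses are equal.

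**Step 4: shorter first phase (ABR 4, CV 1).** With 4 months at 12.5 IU/kg the bias is −7% (pooled) and +6% (mean of patient rates). With 3.5 months it is −3% and +4%.

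**Step 5: the 25 IU/kg rate.** It is unbiased if time at 25 IU/kg is fixed. If total time is held at 13 months instead, early switchers spend longer at 25 IU/kg and the pooled rate there rises too: 4.52 against a true 4.00 at ABR 4 and CV 1, or +13%.

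**Step 6: precision (ABR 4, CV 1).** The relative SD of the 12.5 IU/kg rate is 0.35 to 0.36 in the 3-month window against 0.25 to 0.26 pooled over the whole phase, so the SE is about 40% larger.

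**The case against.** The best case against has several parts.

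- **The display is descriptive.** No 12.5 versus 25 IU/kg test is planned, bleeding is a secondary endpoint, and with 16 patients chance often exceeds the bias. At 2 bleeds a year, equal patient rates and 6 months at 12.5 IU/kg, the SD of the difference in mean patient rates is 0.86 per year against a bias of 0.46. This stands and limits the weight of the point. It does not excuse a systematic error that one extra row would expose.
- **The window is not clearly more accurate.** At ABR 4 and CV 1 the relative RMSE of the 12.5 IU/kg rate is √(0.26² + 0.17²) = 0.31 pooled against 0.36 windowed. For the difference between doses it is 0.30 pooled against 0.35 to 0.36 with 3-month windows on both doses. This stands, and it is why the window should be added and not substituted. A windowed 12.5 IU/kg rate set against the full 25 IU/kg period also gives 0.30.
- **The Cohort 6 SAP may already deal with this.** It is not among the documents. Protocol 9.2 leaves analysis details to the SAP, and a windowed table is still grouped by dose level. A reader might infer that 9.2.2 ties the SAP's hands; it does not.

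Two further inferences go too far. A reader might conclude that all six rates are biased. Only spontaneous bleeds trigger the switch, so the mean patient traumatic rate is unaffected if traumatic bleeds are independent of spontaneous ones. A reader might also conclude that optional switching makes the selection worse. Nothing shows that: if a random half of eligible patients switch, the ABR 4, CV 1 bias roughly halves, to −8% and +7%. Switching guided by a patient's outcome could behave differently.

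**Conclusion.** The point holds as a conditional one. Outcome-dependent switching can distort the whole-phase spontaneous and total rates at 12.5 IU/kg even with no dose effect. For assumed ABRs of 1 to 8 and up to 6.5 months at 12.5 IU/kg, the mean of patient rates is about 5% to 27% too high. The pooled rate is about 2% to 29% too low for CV 0.7 to 1.5, and within about 1% when patients share one rate. The −29% belongs to the extreme corner (ABR 8, CV 1.5), and the bias is smaller with a shorter first phase.

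A reader might infer that a false dose difference is certain, or that its sign is known. The documents support neither: the estimator for Cohort 6 is not fixed, and no bleeding rate or between-patient CV is given for that cohort. The size rests on the Poisson-gamma model and the assumed ranges. The mechanism needs only the switching rule and either averaged patient rates or patients who differ in bleeding rate. This is a cheap improvement, not a flaw that invalidates the study.

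**What to change.** In the Cohort 6 SAP, with a matching sentence in Protocol 9.2.2:

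1. State the estimator (pooled, or mean of patient rates) and how the bleeds and time of early switchers are assigned to dose levels.
2. Next to each whole-phase 12.5 IU/kg rate, show the rate over the first 3 months at that dose, when nobody can switch for bleeding, with the number of patients switched early.
3. Read any 12.5 versus 25 IU/kg or pre-study contrast from this window as well as from the whole phase.
4. Keep the full 25 IU/kg period if its length does not depend on early switching; otherwise show a fixed window there too.

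Separately, the mandatory wording in the Study Outline and Section 3.2 and the permissive wording in Section 5.4 must be reconciled, so that the analysis can describe who switches.

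Cost: SAP wording and one extra table. The windowed 12.5 IU/kg rate has an SE about 40% larger at ABR 4 and CV 1, so it should accompany the whole-phase rate and not replace it.

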Patients with FVIII inhibitors had received OCTA101 doses of 100 IU/kg sc for PK determination followed by 50 IU/kg daily dosing. With 50 IU/kg OCTA101, a mean trough FVIII plasma level of more than 10% was achieved and protected patients from breakthrough bleeds. PK modelling based on the PK data obtained from Cohorts 1 and 3, indicate that doses lower than 50 IU/kg should provide sufficient bleeding control. With 12.5 IU/kg, FVIII trough plasma levels of more than 1% are expected based on modelling, which should protect the patients from breakthrough bleeds. Therefore, following the Nuwiq iv prophylaxis run-in, Cohort 6 will investigate daily prophylaxis with 12.5 IU/kg for 6-7 months, followed by 25 IU/kg (and probably 40 IU/kg) for 6-7 months, based on DMC recommendations.

By introducing a run-in with Nuwiq iv prophylaxis and testing lower doses of OCTA101 sequentially in  $\geq 16$  patients in total, the risk of inhibitor formation should be substantially reduced. However, inhibitor formation will be monitored carefully in Cohort 6, and the study

will be terminated if one more patient develops a confirmed FVIII inhibitor ( $\geq 0.6$  BU) as determined by the central lab.

In conclusion, the existing nonclinical data and the clinical data from Cohorts 1,2, 3 and 5, together with the risk minimization steps implemented in this protocol, indicate that participating in this study should not represent any additional risk to the included patients beyond the possibility of inhibitor formation, for which risk mitigation steps have been taken. ten perm

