### 6.1 Observations by Visit

#### 6.1.1 Screening Visit – All Patients

The following assessments will be performed during the Screening Visit, which should take place within 30 days before the first administration of IMP:

ission

- Obtaining voluntarily given, written (signed and dated) informed consent
- Check of inclusion and exclusion criteria
- Demographics: age, ethnic origin
- Blood type (ABO) •
- CD4+ count
- Medical history ٠
- Details on medications taken within one month before screening, including FVIII it written dosing in the previous 6 months, and any concomitant medications.
- Body weight •
- Height ٠
- Physical examination
- Hemophilia Joint Health Score (HJHS)
- Target joint(s) (defined as three or more spontaneous bleeding episodes into a single joint within 6 consecutive months preceding screening visit)
- Vital signs: systolic and diastolic blood pressure, body temperature, pulse (before blood sample collection)
- Blood sample for FVIII inhibitor measurement (modified Nijmegen Bethesda assay)
- Routine safety lab: Hematology: red blood cell count, white blood cell count, ٠ hemoglobin, hematocrit, platelet count; Clinical chemistry: total bilirubin, ALT, AST, urea, serum creatinine, lactate dehydrogenase
- Start of monitoring of adverse events (AEs)
- Cohort 6: LumiTope assay (negative test result required)

Any bleeding episodes occurring between the Screening Visit and the first exposure to OCTA101 or Nuwig should be treated with the patient's previously used FVIII concentrate.

Following screening, eligible patients will receive a patient diary after the first injection of OCTA101 or Nuwiq. The investigator will explain to the patient how to fill in the diary and will emphasize the importance of carefully documenting all treatment details, adverse events, and concomitant medications.

PK assessments are to be performed after a washout period of at least 72 h, if possible, from the last FVIII injection. Patients must not be experiencing any bleeding.

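### The trough and peak FVIII:C analysis has no rule for samples drawn soon after iv Nuwiq, so Nuwiq activity can be counted as OCTA101 exposure

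*Protocol*

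**What the plan says.** Protocol Section 9.2.2 gives the whole analysis of levels on daily dosing in one sentence: "FVIII:C and OCTA12 trough and peak plasma levels during daily dosing will be analyzed descriptively". SAP Section 8.9.4 does the equivalent for Cohorts 1 to 3 on the full analysis set. Neither mentions time since the last Nuwiq dose.

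For Cohort 6, Protocol Section 5.4 specifies "4-6 weeks prophylactic run-in treatment phase with ~30 IU/kg Nuwiq iv, given 3 x weekly", then daily OCTA101, and adds "No wash-out periods are required between the treatment phases". During OCTA101 dosing, "Nuwiq (according to SmPC) is used to control bleeding episodes, if any". Section 7.2.1.2 has FVIII:C drawn before and 8 h after the first injection and at seven later visits in each dosing period.

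Elsewhere the protocol does guard against carry-over. Section 6.1.1 states "PK assessments are to be performed after a washout period of at least 72 h, if possible, from the last FVIII injection", and Sections 5.4 and 6.1.8 require 72 h from any FVIII injection before the repeat PK profile in Cohorts 1 and 2.

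The levels at issue are low. Section 1.5 says "With 12.5 IU/kg, FVIII trough plasma levels of more than 1% are expected based on modelling", and also "With 50 IU/kg OCTA101, a mean trough FVIII plasma level of more than 10% was achieved".

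**The concern.** The FVIII in OCTA101 comes from the Nuwiq manufacturing process (Section 1.2), and both are measured with the same one-stage and chromogenic activity assays (Section 7.3.5.2). Nothing described in the documents separates the two sources in a plasma sample. A FVIII:C value drawn soon after iv Nuwiq is therefore a sum, and the plan as written would summarise it as an OCTA101 level.

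There are two routes. The run-in can carry over into the first OCTA101 visit, and Nuwiq given for a bleed can fall shortly before any later visit.

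Trough and peak levels are a named secondary endpoint (Section 3.1.2). Section 1.3 says the study will show whether these levels protect against bleeding, and Section 3.3.1 ties the PK results to the choice of Phase 3 regimen. The second route raises measured levels specifically in patients who bled, which would blur the relation between level and protection.

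**Working it through.** **The plan's own figure.** The model behind the 1% figure is not given, so it cannot be reproduced. As a plausibility check, linear scaling of the 50 IU/kg result gives 10% × 12.5/50 = 2.5%, which is consistent with a value above 1%.

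**Inputs.**
- Run-in dose D = 30 IU/kg (Section 5.4).
- Half-life h = 12-14 h (Section 1.1, for FVIII in the circulation generally).
- iv recovery R = 1.5-2.5 IU/dL per IU/kg. This is an assumption, because the documents give no iv figure.
- OCTA101 recovery after a subcutaneous dose: about 0.17 IU/dL per IU/kg, expected from animal data (Section 1.4).

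**Residual Nuwiq activity at time t** = D × R × 0.5^(t/h). The lowest value uses R = 1.5, h = 12; the highest uses R = 2.5, h = 14.

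| Hours since Nuwiq | Residual, IU/dL | Relative to 1% | Relative to 2.5% |
|---|---|---|---|
| 24 | 11.3-22.9 | 11-23 times | 4.5-9 times |
| 48 | 2.8-7.0 | 3-7 times | 1.1-2.8 times |
| 72 | 0.7-2.1 | 0.7-2 times | below 1 |
| 96 | 0.2-0.6 | below 1 | below 1 |

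For example, 30 × 1.5 × 0.5^(48/12) = 45/16 = 2.8, and 30 × 2.5 × 0.5^(72/14) = 75 × 0.0283 = 2.1. The time to fall to 1 IU/dL is h × log2(D × R): 12 × log2(45) = 66 h up to 14 × log2(75) = 87 h.

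**First-injection peak.** If the last Nuwiq dose was 48 h before the first OCTA101 injection, the 8 h sample falls at 56 h and carries 1.8-4.7 IU/dL of Nuwiq. The expected single-dose OCTA101 gain is 12.5 × 0.17 = 2.1 IU/dL.

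**Reach of the run-in.** Taking month 0.5 as day 15 with the 4-day tolerance of Section 6.1.12, the earliest next visit is day 11 (264 h), when the residual is effectively zero. Run-in carry-over therefore reaches only one of the eight visits, in the first dosing period.

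**Effect of one sample.** Take 16 patients with a true trough of 1.0, one of them sampled 24 h after a 30 IU/kg dose, with R = 2.0 (residual 15.0-18.3). The mean becomes (16 × 1.0 + 15.0)/16 = 1.9 to (16 × 1.0 + 18.3)/16 = 2.1 IU/dL.

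**How often bleed treatment matters.** Assume one infusion per bleed, timed independently of visits. The chance that a given sample falls within 72 h after it is 3/365.25 = 0.8% per annual bleed, or roughly 0.8-8% of samples for 1 to 10 bleeds a year. The bleed dose is not given in the documents; for an assumed 20-50 IU/kg, the 72 h residual is 0.5-3.5 IU/dL.

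**The case against.** The strongest reply is that silence is not inclusion. Protocol Section 9 and SAP Section 4 place the Cohort 6 analysis in a separate SAP that was not supplied, and it may contain a rule. This stands, and it is why the point concerns a gap in the text rather than a known error in the results.

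A reader might infer that OCTA101 troughs will be inflated several-fold in every Cohort 6 patient. The documents do not support that:
- The residual depends entirely on hours since the last Nuwiq dose, which no section gives. Dosing three times weekly implies intervals of about 48-72 h, so the 24 h figure need not apply to the run-in.
- The wash-out sentence follows the description of the OCTA101 dose steps, so its application to the change from run-in is the natural but not the only reading.
- The modelled trough is given as a lower bound, not as a value near 1%.
- The sample before the first injection precedes any OCTA101, and nothing says that it counts as a trough.

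A reader might also infer that poor protection would be made to look like good exposure. That is possible for single samples but has not been shown. On the assumptions above the affected share is small, and Section 9.2.2 reports bleeding rates directly by dose.

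Some safeguards exist. The synopsis has levels listed and plotted by patient, and SAP Section 8.9.4 adds displays by visit. These help a reader see outliers but do not alter the summary statistics. Baseline subtraction (Section 9.2.2; SAP Section 8.9) is written among the non-compartmental conventions in the protocol, though the SAP states it generally. Applied here, it would over-correct the first 8 h value because Nuwiq keeps decaying, and it would not address bleed treatment. The SAP otherwise drops only unscheduled-visit data.

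For Cohorts 1 to 3 the bleed route is limited, since Section 9.2.2 reports bleeds only in patients with antibodies or after daily dosing. However, Cohort 1 used Nuwiq prophylaxis before daily OCTA101, and Cohort 3 switched to Nuwiq after about a month.

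**Conclusion.** The concern holds as a gap in the analysis rules. Followed literally, the plan lets FVIII:C from iv Nuwiq enter the OCTA101 trough and peak summaries, at the first OCTA101 visit and after bleed treatment near any later visit. The excess is several-fold only when Nuwiq was given within about 48 h or less. Near 48 h, that description holds against the 1% bound but weakens to 1.1-2.8 times against the scaled 2.5%. By 72 h the residual is comparable with the 1% bound and below 2.5%.

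These sizes rest on the assumed iv recovery, on a general FVIII half-life, and on Nuwiq-to-sample intervals that the documents do not state. The endpoint is secondary and descriptive, and no section makes 1% a success criterion. This is a cheap improvement, not a flaw that undermines the study.

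**What to change.** In Protocol Section 9.2.2 and the Cohort 6 SAP:

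1. Derive time since the last Nuwiq injection for every FVIII:C sample.
2. Report first-injection samples separately from on-treatment visits.
3. Base the main OCTA101 trough and peak summary on samples at least 72 h after Nuwiq, matching the protocol's own wash-out. Repeat it with a 96 h window as a check, because about 2 IU/dL can remain at 72 h after 30 IU/kg.
4. Flag and list the excluded samples, and give the all-samples summary alongside.

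The cost is SAP and protocol wording plus one derived variable. Injection dates and times are already recorded (Sections 5.7.2 and 7.2.1.1). The downside is that a few values are lost, mostly from patients who bleed and who may have the lowest levels. That selective loss is why both summaries should be shown. Dosing and bleed treatment are unchanged.
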